3.4 Randomization and blinding

This is a non-randomized device trial.

3.5 Efficacy endpoints

3.5.1 Primary endpoint

The primary endpoint is implant survivorship at 10 years post study procedure.

The KM survivorship estimate for the DOD group in the PMA cohort at 3 years is 99.3% (95%CI: 97.4%-100.0%). Since this Post-Approval Study (PAS) is intended to document the long-term survivorship of the DOD treatment group only and no comparison to a control is required, no formal statistical hypothesis testing will be conducted.

3.5.2 Secondary efficacy endpoints

Secondary endpoints will be evaluated at 10 years post study procedure and include the following:

- Patient outcomes as measured using the modified Harris Hip Score;;
- Radiographic evaluation to assess radiographic success defined as:
 - -No radiolucencies greater than 2 mm in 50% or more in any of the cup or stem zones; and
 - -No femoral or acetabular subsidence greater than or equal to 5mm from baseline; and
 - -No acetabular cup inclination changes greater than 4 degrees (4°);

3.6 Safety endpoints

Adverse events, noted by study staff and reported by the subject, and occurring from the time of study device implantation through to study completion should be recorded on the appropriate CRFs.

4. Statistical Analysis

Protocol Number: TBD Version 0.3

Forms							
Title	Title Statistical Analysis Plan Template						
Co	Code Version Effective Date Page						
FRM_S	FRM_ST03_032 0.3 23 Apr 2015 8 of 12						

4.1 General

Categorical variables will be summarized with the number and percent of subjects in each group. Continuous variables will be summarized with the mean, standard deviation, median, minimum, and maximum values. 95% confidence intervals will be calculated for the primary and secondary endpoints.

All data collected in the CRF will be presented in the listings.

4.2 Analysis populations

4.2.1 Enrolled set

All study sites and subjects have been recruited and enrollment is closed. DOD cohort subjects that were included in the PMA will continue to be followed as per the follow-up schedule established in the European Post-market Study until they reach the 10-year postoperative interval.

4.3 Software

SAS® v9.2 or above will be used to analyse the data.

4.4 Handling of missing and incomplete data

The number of patients with missing data will be presented under the "Missing" category, if present.

When continuous data are being summarized, only the non-missing values will be evaluated for computing summary statistics.

A sensitivity analysis will be carried out comparing results of the original analysis to the results of an analysis where all missing data are assumed to be failures.

A second sensitivity analysis will be carried out using multiple imputation of the missing data in the form of a tipping point analysis. Multiple scenarios will be analyzed, each with a different number of missing data points imputed as successes for each treatment group. (Missing data points not imputed as successes will be imputed as failures.) The purpose of the analysis is to find the tipping point where a certain number of success imputations for each treatment group causes the inference to reverse.

In general, partial dates will be imputed as follows:

- if only the day is missing, the first day of the month will be assumed;
- if the day and the month are missing, January 1st will be assumed;
- if a date is completely missing or unknown the patient's data will not be included for analysis

Protocol Number: TBD Version 0.3

Forms							
Title	Title Statistical Analysis Plan Template						
Co	Code Version Effective Date Page						
FRM_S	FRM_ST03_032 0.3 23 Apr 2015 9 of 12						

5. Evaluation of Demographic and Baseline Characteristics

Given the nature of this study, the demographic data have been already obtained. The demographic and baseline characteristics will be summarized using descriptive statistics for the Enrolled Set.

6. Patient Accounting

Patient accounting will be presented according to the recommendations in the FDA guidance entitled "Clinical Data Presentations for Orthopedic Device Applications".

- Actual A: Subjects with complete data for the primary endpoint, evaluated per protocol, in the window time frame.
- Actual B: Subjects with any follow-up data reviewed or evaluated by investigator ("all evaluated" accounting).
- Theoretical: Number of subjects that would have reached the beginning of the study window associated with each visit if all subjects returned.
- Deaths: Cumulative number of subjects that died during or prior to the study visit.
- Failures: Cumulative number of subjects that failed (revision) during or prior to the study visit.
- Expected: Theoretical subjects minus the number of deaths and revisions.
- Follow-up Rate: Actual A/Expected*100

Patients discontinued from the study prematurely will be presented, with a breakdown of the reasons for discontinuation as reported in the CRF.

7. Evaluation of Efficacy

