7.1 Analysis of primary endpoint

The primary endpoint is implant survivorship at 10 years post study procedure.

Since this Post-Approval Study (PAS) is intended to document the long-term survivorship of the DOD treatment group only and no comparison to a control is required, no formal statistical hypothesis testing will be conducted.

Implant survivorship will be measured from time of surgery to time of the first instance of removal of any device component for any reason. Subjects who do not experience a removal for any reason will be censored at the date of last data collection.

Protocol Number: TBD Version 0.3

Forms					
Title Statistical Analysis Plan Template					
Code		Version	Effective Date	Page	
FRM_ST03_032		0.3	23 Apr 2015	10 of 12	

Kaplan-Meier (KM) estimates will be provided by time point (life tables) and graphically (survival curves).

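### SAP 4.4 moves partial removal dates earlier with no lower bound, so a removal known only by year can be dated before a contact with the implant in place, or before 10.0 years when it came later

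*Combined protocol and SAP*

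**What the plan says.** SAP 4.4 opens its date rule with "In general, partial dates will be imputed as follows". Two rules for partial dates follow: "if only the day is missing, the first day of the month will be assumed", and "if the day and the month are missing, January 1st will be assumed". A third covers dates with nothing known: "if a date is completely missing or unknown the patient's data will not be included for analysis". Despite the general wording of the opening, no exception or separate rule for removal dates follows. Nothing ties an imputed date to surgery, to the last contact with the implant in place, or to the 10-year landmark. PAS protocol section 9.1 repeats the survivorship definition and adds no date rule.

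SAP 7.1 makes the removal date part of the primary outcome: "Implant survivorship will be measured from time of surgery to time of the first instance of removal of any device component for any reason". The landmark is fixed there too: "The primary endpoint is implant survivorship at 10 years post study procedure". The same section gives Kaplan-Meier estimates by time point, so intermediate years are reported as well. SAP 3.2 allows the 10-year visit within 6 months either side, so removals shortly after 10.0 years can be recorded.

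**The concern.** Both partial-date rules move a date earlier or leave it unchanged; neither can move it later. A removal date filled in this way enters the Kaplan-Meier analysis directly, and two things can go wrong.

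1. The imputed date can contradict the study's own records. A removal known only by year goes to 1 January, even if a visit or telephone contact later that year found the implant in place.
2. The imputed date can cross the landmark. A removal after 10.0 years, known only by year, can be pulled back before 10.0 years and counted as a primary-endpoint failure.

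At stake are the accuracy of the 10-year estimate and of the estimates at earlier time points, in a cohort with few expected events. The information that would prevent the first error is already collected: clinic visits, and the telephone form, which asks about component removal since the last visit. The rule does not use it.

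**Working it through.** **Inputs.** The two date rules (SAP 4.4); survivorship from surgery to first removal, with a 10-year landmark (SAP 7.1); 10-year window of 6 months either side (SAP 3.2); 137 DOD subjects, of whom one had died and one was revised by year 3, leaving 135 carried forward (SAP 3.1). The documents do not project the number at risk at year 10; 90 is an assumption.

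**Step 1: size of the shift.** Applying the rules to each of 365 calendar days:
- day missing: mean 14.7 days early, maximum 30;
- day and month missing: mean 182 days early, maximum 364 (365 in a leap year).

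**Step 2: worked dates** (assumed surgery date 14 May 2010).
- The implant is in place at a visit on 14 May 2015 and is removed on 10 October 2015, with only the year known. The imputed date is 1 January 2015, 133 days before that visit. The removal moves from 5.41 to 4.64 years and becomes a failure before year 5.
- Removal is on 10 September 2020 (10.33 years), with only the year known. The imputed date is 1 January 2020 (9.63 years), and the removal becomes a failure before year 10.

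**Step 3: how often the landmark is crossed.** Let the 10-year anniversary fall evenly over the calendar year and the removal follow it by U years, with U uniform on 0 to 0.5. The imputed date precedes the anniversary when both fall in the same calendar year:

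P = 1 − E(U) = 1 − 0.25 = 0.75.

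Enumerating all 365 anniversaries against removals 1 to 182 days later gives 74.7%. If only the day is missing, the figure is 7.6%. The year-only rule is therefore the one that matters.

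**Step 4: effect on the estimate.** One added event lowers the Kaplan-Meier estimate by S/n, where S is survival just before it and n the number at risk. As a check, the SAP's 3-year figure of 99.3% with one revision among 137 is 1 − 1/137 = 99.27%. With S close to 1:
- n = 137: 1/137 = 0.73 points;
- n = 90 (assumed): 1/90 = 1.11 points.

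Taking S = 0.97 instead gives 0.97/137 = 0.71 and 0.97/90 = 1.08 points, so the rounded figures stand.

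**The case against.** **Such dates should be rare.** A positive answer on the telephone form leads to the Adverse Event CRF, which asks for day, month and year of removal or revision and is signed by the investigator. A year-only date for hip revision surgery is possible but would be exceptional. This stands, and it limits the weight of the point. The documents do not say how many dates are partial.

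**The error is conservative.** For removals, the rule can only lower estimated survivorship, and SAP 7.1 plans no formal test that could change its result. This also stands. It does not make the date right in a study whose purpose is to document long-term survivorship.

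**The planned sensitivity analyses might cover it.** They do not. Those in SAP 4.4 vary whether missing outcomes count as successes or failures. A partial date is filled in, so its timing is never varied.

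Two stronger readings are tempting and fail.
- *Peri-operative adverse events might be lost.* An event in the month of surgery with the day missing would usually be dated before surgery, and SAP 3.6 speaks of events "occurring from the time of study device implantation through to study completion". But that is an instruction on what to record. The counts in SAP section 8 are taken over the enrolled set with no date filter, so the event is still counted.
- *A removal might get a negative survival time.* The 135 subjects carried forward were unrevised at year 3 and the shift is at most 365 days, so their removals cannot be dated earlier than about 2 years after surgery. The only other removal is the single revision by year 3. It is already in the reported 3-year estimate, and nothing suggests that its date is partial.

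**Conclusion.** The point holds as a minor one. SAP 4.4 can give a removal a date that the study's own records contradict, or place it on the wrong side of year 10. The second error affects about 75% of removals at 10.0 to 10.5 years known only by year, if calendar dates are spread evenly. Each one costs about 0.7 points of 10-year survivorship with 137 at risk and about 1.1 with an assumed 90. The direction is always downwards. The documents give no basis for expecting more than a few such dates. The point concerns removals in the primary analysis; the planned safety counts are unaffected.

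**What to change.** Add to SAP 4.4:

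> An imputed postoperative date is never earlier than the date of surgery. An imputed removal date is also never earlier than the last date on which the implant was documented in situ, nor later than the first date on which it was known to be removed. If the possible range of a partial removal date spans 10 years after surgery, the 10-year Kaplan-Meier estimate is also reported with the earliest and the latest possible date.

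In the first worked example the floor moves the removal from 1 January to 14 May 2015, so it no longer contradicts the visit. In the second, the floor helps only if a contact after the anniversary found the implant in place. Otherwise the range spans 14 May 2020, and the estimate is shown both ways.

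A midpoint rule is a natural alternative, but it does not settle the landmark. Suppose the implant was in situ at 7 years and known removed at 10.5 years (both assumed). The midpoint is (7 + 10.5)/2 = 8.75 years. For a removal at 10.0 to 10.5 years the known calendar year cannot begin before 9.0 years, so forcing the midpoint into that year returns 1 January and the same 75%. Restricting the interval to the known year before taking the midpoint leaves 25% of these removals dated early. It also moves 25% of true removals at 9.5 to 10.0 years past year 10, which the current rule never does.

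The change needs no new data. Its only cost is one extra sensitivity run, and only if such a date occurs.

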7.1 Analysis of primary endpoint

The primary endpoint is implant survivorship at 10 years post study procedure.

Since this Post-Approval Study (PAS) is intended to document the long-term survivorship of the DOD treatment group only and no comparison to a control is required, no formal statistical hypothesis testing will be conducted.

Implant survivorship will be measured from time of surgery to time of the first instance of removal of any device component for any reason. Subjects who do not experience a removal for any reason will be censored at the date of last data collection.

Protocol Number: TBD Version 0.3

Forms					
Title Statistical Analysis Plan Template					
Code		Version	Effective Date	Page	
FRM_ST03_032		0.3	23 Apr 2015	10 of 12	

Kaplan-Meier (KM) estimates will be provided by time point (life tables) and graphically (survival curves).

7.2 Analysis of secondary efficacy endpoints

Secondary endpoints include the following:

- Patient outcomes as measured using the modified Harris Hip Score;
- Radiographic evaluation to assess radiographic success defined as:
 - -No radiolucencies greater than 2 mm in 50% or more in any of the cup or stem zones; and
 - -No femoral or acetabular subsidence greater than or equal to 5mm from baseline; and
 - -No acetabular cup inclination changes greater than 4 degrees (4°) and

These endpoints will be summarized using descriptive statistics and presented for all post-operative visits.

8. Evaluation of Safety

The number of AEs, SAEs, USADEs, Reoperation and Revisions, and the number and the percentage of patients experiencing AEs, SAEs, USADEs will be presented for the enrolled set.

The number of AEs and the number and the percentage of patients with at least one AE will be presented for AEs, and SAEs.

The number and the percentage of patients with at least one AE will be presented by severity, seriousness, device relatedness and procedure relatedness.

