9. STATISTICAL PROCEDURES

9.1. General considerations

General summary statistics for numeric data will include the available records (n), the mean, the standard deviation (SD), the median, the minimum, and the maximum value. For categorical data, the count and percent of data will be presented with the percent based on the number of subjects with data. Implant survivorship will be measured from time of surgery to time of the first instance of removal of any device component for any reason. Subjects who do not experience a removal for any reason will be censored at the date of last data collection. Kaplan-Meier (KM) estimates will be provided by time point (life tables) and graphically (survival curves).

The Statistic Analysis Plan is found in Appendix III.

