The formation of ectopic bone is a complication that occurs with a moderate percentage of patients following total hip replacement. AP hip and lateral radiographs will be reviewed for the formation of heterotopic ossification and if present will be graded according to the Brooker Classification. The Brooker classification uses a scale consisting of four levels.⁶ See **Figure 6** for illustration⁷. The amount of heterotopic bone formation will be graded according to the amount of ectopic bone demonstrated on the radiograph, although it is noted that heterotopic ossification classifications are not always associated with reduced postoperative functional results, especially if less than grade III.⁶

Independent Review X-ray Follow up - Years 1, 3, 5, 7 and 10 (Page 2)

On this page of the CRF, radiolucencies, osteolysis, atrophy, and hypertrophy will be assessed in the acetabular and femoral regions. All assessments should involve a comparative evaluation with all pre-existing longitudinal radiographs for a given subject. If no findings are discovered, check "no" in each section and the form is complete.

Otherwise, select "yes" in each section affected by radiolucencies, osteolysis, atrophy, and/or hypertrophy and complete the rest of the form.

Radiolucent lines Negative Omm 1mm 2mm >2mm Zone I	Osteolysis no yes	Atrophy	Hypertrophy minimalmoderate severe none 1mm 2mm >2mm	7 6 5
Radiolucent lines Negative Omm 1mm 2mm>2mm	Osteolysis no yes	Atrophy minimal moderate severe none 1mm 2mm >2mm	Hypertrophy minimal moderate severe none 1mm 2mm >2mm	
Zone 1				V VI 8 14 9 13
Zone 8				10 12

Delineation of Zones:

To differentiate radiographic findings in the femoral stem area, the stem will be divided into numbered zones as described by Gruen, McNeice, and Amstutz (1979)⁸. Zones are illusatrated in the CRF figure above.

- The bone-prosthesis interface of the femoral component in the AP orientation will be divided into 7 zones.
- Corresponding areas in the lateral view of the femoral component will also be divided into seven zones numbered 8-14 to differentiate the specific area and view in which it was noted.
- The acetabular region in the AP projection only will be divided into three zones as described by DeLee and Charnley (1976).9

Radiolucencies:

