Areas of the bone surrounding the implanted device which show low density lines or rounded areas are considered radiolucencies which may indicate areas of potential concern. While radiolucencies can be found in well fixed, asymptomatic total hip replacements, the chance of loosening increases with the extent and thickness of radiolucent areas at the bone-implant interface. In particular, implants with radiolucent areas which appear as continuous gaps around the implant greater than or equal to 2 mm in width have the highest probability of loosening. Radiolucencies observed in varying shapes indicative of localized bone resorption, cystic erosion, increased shear stress, and diffuse linear forms are normally considered to result from expansion of the periprosthetic cortical bone.

Areas of radiolucency in linear form in the zones around the implanted device will be measured and reported, irrespective of root cause (lesions, resorption, shear stress, etc.). Each zone (Figures in CRF above) will be evaluated for radiolucencies and the maximum width of the radiolucent line measured will be noted in whole mm using standard rounding rules (≥2 mm is considered significant). Any observed radiolucencies will be tracked longitudinally.

Osteolysis:

Osteolysis is the dissolution of bone through the active resorption of native bone matrix by osteoclasts as a result of disease, infection, or ischemia. The development of periprosthetic osteolysis is not an uncommon occurrence following joint replacement and is believed to be a secondary response of macrophage activity stimulated by microscopic wear particles released from articulation of components in an artificial hip joint.¹¹ The resulting biological cascade promotes progressive bone degeneration leading to implant loosening or fracture. While originally associated with cemented components, periprosthetic osteolysis has also been demonstrated with non-cemented devices of various materials¹¹ such as ceramics, polyethylene, and metals. In particular components consisting of ultra-high molecular weight polyethylene have shown higher incidence of osteolysis due to increased wear debris.¹² Regardless of the etiology, distinguishable osteolysis or resorption will be documented on the case report form according to the zones in which changes are observed.

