 where Y is the exact (known) value

As a result of these discrepancies, any quantitative measurements performed on the radiographs using the existing CF, could produce a 15-54% error. For example, a measured radiolucent line of 2.2 mm on the lateral image is actually only 1.12 mm. Since the CRF bins radiolucent lines in buckets of "0 up to 1mm", "1 up to 2 mm", and "> 2 mm", data would have been entered incorrectly (a check in the "> 2 mm" box instead of the correct box of "1 up to 2 mm").

To ensure image headers contain an accurate CF, an additional evaluation step will be implemented for all images in this study followed by recalibration if necessary.

Procedure for the Evaluation Step:

Step 1: Each radiograph will be opened (Figure 2). The femoral head of the implant will be magnified (Figure 3) and a best-fit circle will be drawn around the femoral head to determine its diameter in pixels. Three points on the femoral head will be selected in order to create the circle (Figure 4, arrows highlight the 3 points selected).

Step 2: The diameter of the circle in pixels will be calculated and output to a spreadsheet for each image. The image name (containing the patient ID, time point, date of acquisition, and radiographic view) will also be exported with the diameter. In addition, the type of image (DICOM or TIFF) and original embedded scale factor (for DICOM only) will be copied from the headers into the spreadsheet.

Step 3: The actual diameter of the femoral head for each implant, as reported by S&N's product development team, will be reported in the same spreadsheet. The diameter is specific to the implant size and material (Table 1) and is specific to the individual patient.

Step 4: The CF will be calculated by dividing the actual femoral head diameter (in mm) by the diameter of the head (in pixels) measured in Step 1. The resulting number is the CF in units of mm/pixel. This number will allow conversion between pixels and mm for any measurement on a given image. Figure 5 is a snapshot of the spreadsheet layout.

[figure not shown]

Table 1: Femoral Head Diameters

Figure 5	Size	Outside Diameter (mm)
	28	27.9
	32	31.9
OXINIUM	36	35.9
	40	39.9
	44	43.9
	22	22.2
	26	25.9
	28	27.9
CoCr	32	31.9
	36	35.9
	40	39.9
	44	43.9
	28	28.0
Biolox Forte	32	32.0
	36	36.0
	28	28.0
Biolox delta	32	32.0
	36	36.0

Image Name	File Type	Reported Pixel Spacing (mm)	Known Length (mm)	Measured Length (pixels)	Actual Pixel Spacing (mm)

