Sta	foot over foot, without banister foot over foot, with banister in any manner unable				
Inv	estigator's Signature:	4.1-			Month Year
	Piease fax	uns page as	soon as complete	ea	

Plate # U81

Visit # 320 10 Year

Independent Review X-ray Follow-up

(page 1 of 2)

Project No.: F	₹3		
Study Patient No:			

5000	(page 1 61 2)
General Findings	Date of Radiograph: Day Month Year
migration medial r	Stem position ** unchanged varus tilted valgus tilted subsidence mm subsidence mm subsidence mm
stable fibrous ingrowth unstable implant **Compared to baseline post-o	perative
Heterotopic ossification (Brooke	r Classification) (Tick one box only)
☐ Grade 0 none, no islands of bo ☐ Grade I islands of bone within ☐ Grade II bone spurs from the p bone surfaces	the soft tissues about the hip elvis or proximal end of the femur leaving at least 1 cm between opposing pelvis or proximal end of the femur, reducing the space between opposing
Investigator's Signature:	Date: Day Month Year
	Please fax this page as soon as complete

I		I			I		I		Ī		Ī	Ī	ĺ	1	Ì	

Plate # 093

Visit # 320 10 Year

> smith&nephew

Independent Review X-ray Follow-up

(page 2 of 2)

Project No.:	R3		
Patient No:			

Radiographic Evaluation					
Radiolucent lines	Osteolysis	Atrophy		Hypertrophy	
Negative		ı 🗆		, . ,	
0mm 1mm 2mm >2mm	no yes				
Zone I 🔲 🔲 🔲					
Zone II 🔲 🔲 🔲]
Zone III					1 7
Zone IV 🔲 🔲 🔲					2 6
Zone V 🔲 🔲 📗					3 5
Zone VI 🔲 🔲 🔲					
Radiolucent lines	Osteolysis	Atrophy		Hypertrophy	4
Negative					
0mm 1mm 2mm>2mm	no yes	minimal modera none 1mm 2mm	te severe >2mm	minimal moderate se none 1mm 2mm >2	vere mm
Zone 1]
Zone 2					_
					_
					IV VI
Zone 7					8 14
Zone 8					9 13
Zone 9 🔲 🔲 🔲					
Zone 10					10 12
Zone 11] 11
Zone 12]
]]
			Ц		-
Notes:					
Investigator's Signature:			_	Date:	
	Plea	se fax this page as s	oon as co		Month Year
	Radiolucent lines Negative	Radiolucent lines	Radiolucent lines	Radiolucent lines	Radiolucent lines

				1	1				

Plate # 099

Missed Visit/ Telephone Follow-up

Project No:		R3
Study Patient No:		

	Telephone Follow-up	Patient No:				
Interval Missed: 3 Months 5 Years Use this form for subjects still on study	1 Year 3 Years D 7 Years 10 Years	Pate of Report: Day Month Year World Visit.				
Reason Missed: (Tick one box only)						
Illness	Patient contacted and is feeling fine but do	pes not want to be examined				
Patient on vacation	Long difficult traveling distances					
Patient moved	Business commitments					

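### Radiographic success in the post-approval study turns on how much of a zone a lucent line covers, but the reader records only its width, so some hips cannot be classified

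*Combined protocol and SAP*

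**What the plan says.** Radiographic success is defined in PAS addendum 2.2 and repeated in SAP 3.5.2 and 7.2. All three parts must be met: "No radiolucencies greater than 2 mm in 50% or more in any of the cup or stem zones"; no cup or stem subsidence of 5 mm or more; and no change in cup inclination above 4 degrees. SAP 3.5.2 sets the time point ("Secondary endpoints will be evaluated at 10 years post study procedure"), and SAP 7.2 also asks for a descriptive summary at every postoperative visit. SAP 4.1 attaches 95% confidence intervals.

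One central radiologist reads the films under the Image Evaluation Protocol. Its Radiolucencies section says of each zone that "the maximum width of the radiolucent line measured will be noted in whole mm using standard rounding rules". Page 2 of the Independent Review X-ray Follow-up form gives one tick per zone on the scale "0mm 1mm 2mm >2mm". Appendix B of the image protocol, which deals with image scaling, also describes this field purely as widths: "Since the CRF bins radiolucent lines in buckets of" 0 to 1, 1 to 2, and over 2 mm.

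On zones, the image protocol states: "The acetabular region in the AP projection only will be divided into three zones". It gives the stem seven AP and seven lateral zones. The form lists six cup zones and 14 stem zones.

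PAS addendum 9.1 reports categorical results "with the percent based on the number of subjects with data". SAP 4.4 plans a sensitivity analysis in which "all missing data are assumed to be failures", followed by a tipping-point analysis.

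**The concern.** The lucency part of the rule needs two facts about each zone: whether the line is wider than 2 mm, and whether it covers at least half. Only the first is collected. The image protocol itself links loosening risk to both extent and thickness, yet it gives no instruction to measure extent, and the SAP gives no rule for deriving it from the width ticks.

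The analyst would have to choose a rule for the hips with the widest recorded lucent lines. The same films could then yield different 10-year success rates for a named secondary endpoint of a study that PAS addendum 1.1 describes as a condition of FDA approval. If hips that cannot be classified are treated as having no data, the denominator could change as well.

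**Working it through.** The plan states no radiographic success rate, so there is no figure to reproduce. The check compares what the rule needs with what is recorded, then bounds the effect.

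**1. Needed against recorded, for each zone**
- Width above 2 mm: needed by the success rule and recorded as a tick.
- Extent of at least 50%: needed by the success rule. Neither the image protocol nor the 5-, 7- or 10-year form has a field or instruction for it. The form has a free-text notes box, but the reader is not told to put lucency extent there.

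**2. Which hips this leaves undetermined**
- A hip that fails on subsidence or inclination is a failure whatever its lucency, so it can be classified.
- A hip that passes those two parts, with every zone ticked 0 or 1 mm, is a success.
- A hip that passes those two parts but has at least one zone ticked over 2 mm cannot be classified, because extent decides the result.

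**3. The width cut**
- Under whole-millimetre rounding (Radiolucencies section), 2.1 to 2.4 mm rounds to 2 and goes in the 2 mm box. A width of 2.5 mm rounds to 3 and goes in the over-2 mm box.
- Appendix B uses a reading of 2.2 mm as an example of a value that would be ticked over 2 mm.
- So 2.2 mm escapes the lucency rule under one instruction and is caught by it under the other. If a visit was read with rounding, hips with a 2 mm tick that pass the other two parts are also undetermined.
- The Radiolucencies section calls 2 mm or more significant, while the endpoint uses more than 2 mm.

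**4. Size**
Let n be the readable hips, f the failures on subsidence or inclination, and u the undetermined hips.
- All undetermined hips fail: (n − f − u)/n
- None fail: (n − f)/n
- Gap: u/n

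The documents give 135 eligible subjects (SAP 3.3); I take one study hip each. I also use n = 135 × 0.8 = 108, an assumed 20% loss. The value of u is not in the documents, so a range is shown.

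| u (assumed) | gap, n = 135 | gap, n = 108 |
|---|---|---|
| 0 | 0 | 0 |
| 1 | 0.7 points | 0.9 points |
| 3 | 2.2 | 2.8 |
| 5 | 3.7 | 4.6 |
| 10 | 7.4 | 9.3 |

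Some hips ticked over 2 mm will already have failed on another part. The number of such ticked hips divided by n is therefore only an upper bound on the share of the gap that comes from those ticks.

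**5. Denominator, one assumed example: n = 108, f = 3, u = 5**
- All undetermined fail: 100/108 = 92.6%
- None fail: 105/108 = 97.2%
- Undetermined hips dropped: 100/103 = 97.1%

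In this example, dropping them gives almost the same rate as calling them all successes.

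**The case against.** Four points can be made against this.

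First, the 50% might be read as a share of zones, which can be counted from the ticks. The phrase about any of the zones points instead to extent within a zone, and the SAP sets no counting rule. Nor would that reading settle the matter. Lines in two AP cup zones are 2/3 = 67% of the image protocol's zones but 2/6 = 33% of the form's. Lines in four AP stem zones are 4/7 = 57% of the AP zones but 4/14 = 29% of all stem zones. These percentages show only that the alternative reading does not help; they do not measure the main gap. The six cup zones on the form appear to be three AP plus three lateral, so the mismatch with the image protocol is one of wording and easily cleared up.

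Second, a reader might infer from SAP 4.4 that every undetermined hip will be counted as a failure in the sensitivity analysis. The text does not go that far. A tick over 2 mm is recorded data, so this follows only if the analyst codes the hip as missing. In that case the planned tipping-point analysis, which varies how many are imputed as successes, would already cover much of the range between the bounds. Loss from the denominator under PAS addendum 9.1 is likewise only a possibility.

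Third, no impact is shown. The number of affected hips is unknown, the endpoint is descriptive, and no success threshold or test depends on it. This stands, and it limits the weight of the point.

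Fourth, PAS addendum 1.1 says that data collection stays on the original study's forms, and changing the width rule now could break comparability with visits already read. This stands as a cost, and it is why a remedy limited to zones ticked over 2 mm would be too narrow.

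**Conclusion.** The point holds. Following the plan exactly, the lucency part of radiographic success cannot be derived for a hip that is ticked over 2 mm and passes the other two parts. The conflicting width rules add uncertainty for widths between 2.0 and 2.5 mm. Each undetermined hip is worth 0.7 points at n = 135, or 0.9 at an assumed n = 108. The total may be zero.

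Two stronger readings are tempting but not supported. One is that every hip ticked over 2 mm is unclassifiable; those that already fail on subsidence or inclination are not. The other is that a hip without such a tick is a sure pass; under whole-millimetre rounding its 2 mm ticks may hide widths of 2.1 to 2.4 mm.

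Nothing here affects the primary endpoint, 10-year implant survivorship. The conclusion assumes that the forms shown are complete and that the 50% refers to extent within a zone. The gap is worth closing before the 7- and 10-year films are read.

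**What to change.** - In PAS addendum 2.2 and SAP 3.5.2 and 7.2, state that the 50% is a share of the length of the zone concerned. Name the cup zones used: three AP, or three AP plus three lateral.
- In the Image Evaluation Protocol, state that the over-2 mm box is ticked for any measured width above 2.0 mm before rounding, and bring Appendix B into line.
- On the 7- and 10-year reader forms, add a tick for under 50% or at least 50%, completed only for zones ticked over 2 mm.
- For visits already read, either have the same reader re-read the zones ticked 2 mm or over 2 mm, or report two rates (all undetermined hips fail; none fail).
- In either case keep these hips in the denominator. The three-part success rule stays as it is.

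The cost is a change to the visit-specific bar-coded forms, covering up to 6 + 14 = 20 zones although few ticks should be needed, despite the plan to keep the original forms. FDA and ethics committee approval may be needed (PAS addendum 10.2). There is also a small targeted re-read, which reporting bounds would avoid. No new films are required. As the image protocol stands, the reading contract for 7 and 10 years is still to be made, so the change can be written into it.
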